### **6.3 Laboratory Assessments**

#### **6.3.1 Collection of Blood Samples**

Additional blood samples may be done at the discretion of the investigator (or qualified designee), if (for example) an AE is suspected (see Section 7).

#### **6.3.2 Laboratory Results Outside the Normal Range**

All laboratory values that fall outside the reference range and are of potential clinical relevance should be noted and commented upon by the investigator (or qualified designee). The appearance of abnormal laboratory results or significant shifts from VTV, considered to be clinically significant by the investigator (or qualified designee) are to be documented as an AE (see Section 7.1.1). Any abnormal laboratory results obtained should be considered by the investigator (or qualified designee) as related to previous use of pridopidine in Open-HART, in which case they will be considered treatment-emergent AEs.

Calcium, magnesium, and potassium levels will be drawn every 6 months [hypokalemia is defined as a potassium level of <3.5 mEq/L]. If <3.5 mEq/L, patient's study drug will be suspended until normal ( $\geq 3.5$  mEq/L).

If hypokalemia is observed, dosing will be interrupted and should not be started again until normal electrolyte values are confirmed by re-draw and maintained for 7 days. Patients needing more than 14 days to reach stable potassium levels, without IMP, should be withdrawn from IMP. The patient will be asked to continue in the study and follow the visit schedule as outlined in the protocol.

[REDACTED], and to ensure a reasonable minimum clearance in all patients through the renal pathway, patients with a creatinine clearance <60 mL/min (calculated by the Cockcroft-Gault formula) will be excluded from the study or may be able to take a lower dosage of IMP (45 mg qd) if his/her creatinine clearance is <60 mL/min and >40 mL/min, per discretion of the investigator (or qualified designee). Patients that de-escalate to half-doses of IMP will have creatinine clearance monitored more frequently than patients at the full dose, as determined by the investigator (or qualified designee). Patients will be discontinued from treatment with IMP if their creatinine clearance decreases to <40 mL/min during their participation in the study. The test may be repeated once, if clinically appropriate.

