### **7 SAFETY PARAMETERS AND ADVERSE EVENTS**

#### **7.1 Definitions**

##### **7.1.1 Adverse Event (AE)**

An AE is defined as any untoward medical occurrence in a patient or clinical study subject administered a medicinal product and which does not necessarily have a causal relationship with this treatment. An AE can therefore be any unfavorable and unintended sign (including an abnormal laboratory finding), symptom, or disease temporally associated with the use of a medicinal (investigational) product, whether or not related to the medicinal (investigational) product.

This definition includes accidental injuries, study drug intolerance, overdosing, reasons for any unplanned change in medication (drug and/or dose), reasons for any medical, nursing or pharmacy consultation, or reasons for admission to hospital or surgical procedures. It also includes AEs commonly observed and AEs anticipated based on the pharmacological effect of the IMP. In addition, any laboratory abnormality assessed as clinically significant by the investigator (or qualified designee) must be recorded as an AE.

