##### **7.1.3 Treatment-Emergent Adverse Event**

A treatment-emergent AE is any AE occurring after start of IMP and within the time of residual drug effect, or a pre-treatment AE or pre-existing medical condition that worsens in intensity after start of IMP and within the time of residual drug effect.

The time of residual drug effect is the estimated period of time after the last dose of the IMP, where the effect of the product is still considered to be present based on PK, pharmacodynamics, or other IMP characteristics. The time of residual drug effect is for most drugs 5 half-lives of the IMP.

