### 7.2.2.3 Causal Relationship to the IMP

The reporter must always report his/her evaluation of causal relationship between the event and the suspect drug. The causal relationship to the IMP must be rated using the following 2-point scale:

Term	Definition	Clarification
No reasonable possibility (not related)	This category applies to AEs which, after careful consideration, are clearly due to extraneous causes (disease, environment, etc.) or to AEs, which, after careful medical consideration at the time they are evaluated, are judged to be unrelated to the IMP.	An AE may be considered no reasonable possibility if it is clearly due to extraneous causes or when (at least 2 of the following): 
 
• it does not follow a reasonable temporal sequence from the administration of the IMP.
 
• it could readily have been produced by the patient's clinical state, environmental or toxic factors, or other modes of therapy administered to the patient.
 
• it does not follow a known pattern of response to the IMP.
 
• it does not reappear or worsen when the IMP is re-administered.
 

Reasonable possibility (related)	This category applies to AEs for which, after careful medical consideration at the time they are evaluated, a connection with the test drug administration can neither be ruled out with certainty nor felt with a high	An AE may be considered reasonable possibility related if or when (at least 2 of the following): 
 
• it follows a reasonable temporal sequence from administration of the IMP.
 
• it cannot be reasonably explained by the known characteristics of the patient's clinical state, environmental or toxic factors, or
 

	degree of certainty to be related to the IMP.	other modes of therapy administered to the patient. 
 
• it disappears or decreases on cessation or reduction in dose. There are important exceptions when an AE does not disappear upon discontinuation of the drug, yet drug-relatedness clearly exists.
 
• it follows a known pattern of response to the IMP.
 

--	---	---

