### **7.6.2 Expedited Reporting**

All AEs that are **serious, unexpected, and considered related to the IMP** judged by either the investigator (or qualified designee) or Teva require expedited reporting.

The expectedness is assessed by Teva according to the (Investigator's Brochure) IB in force at the time of the event.

All available information relevant to the evaluation of the SAE will be reported.

SAEs will be considered reportable regardless of whether or not the IMP was used in accordance with the provisions in the Protocol and/or the IB.

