### **7.3. Adverse Events**

All AEs will be coded using the MedDRA. AEs occurring on or after the first day of study drug administration will be included in the summaries. Summaries will be presented for all AEs (overall and by severity), AEs determined by the investigator to be related to study drug (overall and by severity), serious AEs, AEs leading to withdrawal from the study, and non-serious AEs.

The incidence and total number of AEs will be summarized using descriptive statistics by SOC and PT (all AEs overall will also be presented by just PT category). For the incidence of AEs, patients are counted only once in each SOC category, and only once in each PT category. The exposure adjusted incidence rate will also be presented and is defined as the number of patients with an AE divided by patient-years of treatment. For calculating patient-years, patients with an AE contribute with treatment exposure up to the day of their first AE, and patients without an AE contribute with the entire treatment exposure. For the summary by severity, patients are counted at the greatest severity. AEs missing relationship to study drug will be included in the study drug related summary.

In addition, a summary of AEs by time period of treatment will be presented.

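### Protocol Section 6.3.2, as printed, presets abnormal laboratory results as drug-related, against the case-by-case causality rating; if followed, it would bias the related-AE summaries upward by an amount the documents do not allow us to derive

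*Protocol*

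**What the plan says.** Protocol Section 6.3.2 first sets a filter: abnormal results or shifts from the Virtual Transition Visit (VTV) that are "considered to be clinically significant by the investigator (or qualified designee) are to be documented as an AE". Section 7.1.1 repeats it: "any laboratory abnormality assessed as clinically significant by the investigator (or qualified designee) must be recorded as an AE". The next sentence of Section 6.3.2 then reads "Any abnormal laboratory results obtained should be considered by the investigator (or qualified designee) as related to previous use of pridopidine in Open-HART", followed by "in which case they will be considered treatment-emergent AEs".

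Other sections treat the same matters differently:

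- **Causality.** Section 7.2.2.3: "The causal relationship to the IMP must be rated using the following 2-point scale". The table there lists criteria for each category and asks for at least two of them, or, for an unrelated event, a clear external cause.
- **Treatment-emergence.** Section 7.1.3: "A treatment-emergent AE is any AE occurring after start of IMP and within the time of residual drug effect", or a pre-existing condition that worsens in that window. Section 8.9.2 also goes by onset relative to dosing.
- **Use of the rating.** Protocol Section 8.9.2 tabulates AEs by relationship to IMP. SAP Section 7.3 plans a separate summary of AEs that the investigator determined to be related, overall and by severity. Under protocol Section 7.6.2, AEs that are serious, unexpected and related, "judged by either the investigator (or qualified designee) or Teva require expedited reporting".

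**The concern.** The sentence tells the investigator what to conclude. An abnormality with an evident other cause has to be called related under Section 6.3.2 and may be called not related under Section 7.2.2.3, and a site cannot do both. The sentence also says *any* abnormal result, so it is unclear whether the clinical-significance filter of the preceding sentence still applies.

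Long-term safety is a primary objective. The SAP lists no laboratory measure among its safety measures (Section 2.3) and plans no laboratory summary in Section 7, so the AE tables are the only route it sets out by which laboratory findings reach the report. A rating fixed in advance carries no information about the drug, and the related-AE table takes the rating as given.

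Relatedness also drives three operational rules in the protocol: AE follow-up after end of study (Section 7.3), reporting of SAEs learned of after end of study (Section 7.5.3.1) and expedited reporting (Section 7.6.2). In the last, either the investigator's or the sponsor's judgement is enough, so sponsor review cannot undo a default rating.

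**Working it through.** The plan gives no figure to reproduce. It states no laboratory abnormality rate, no laboratory AE rate and no related-AE rate. The check is therefore a side-by-side reading, followed by one case traced through the rules.

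**Step 1. The passages compared**

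| Question | Disputed sentence, protocol 6.3.2 | Rest of the plan |
|---|---|---|
| Which results become AEs? | Any abnormal result, no filter stated | Only those judged clinically significant (6.3.2 preceding sentence; 7.1.1) |
| Who decides causality, and how? | Set to related in advance | Rated event by event on two categories (7.2.2.3) |
| What makes an AE treatment-emergent? | Follows from being related | Timing or worsening (7.1.3); onset relative to dosing (8.9.2) |
| Which AEs enter the tables? | Silent | Onset on or after the first day of study drug (SAP 7.3) |

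The second and third rows are contradictions. The first row is an ambiguity.

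**Step 2. One case traced.** Take a clinically significant low calcium that starts on drug and has a clear other cause.

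- *Site follows 6.3.2:* rated related. The event enters the all-AE and the related-AE summaries.
- *Site follows 7.2.2.3:* rated not related. The event enters the all-AE summary through its onset date and stays out of the related-AE summary.
- *Treatment-emergence:* met on both routes under 7.1.3 and 8.9.2. The AE log items in protocol Section 7.2.1 include onset date and causality but no treatment-emergent flag, so the site does not decide that status.
- *If the event were also serious and unexpected:* the first route meets the expedited-reporting condition. The second does so only if the sponsor judges it related.

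**Step 3. Direction of the bias.** Let R be the number of patients with at least one AE rated related when every event is rated case by case. Let D be the number who have an on-drug laboratory AE but no AE that case-by-case rating would call related. If all sites follow the sentence, the related count is R + D. Since D cannot be negative, the error is upward or nil. The same holds within each system organ class or preferred term row.

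SAP Section 7.3 defines an exposure-adjusted rate in which a patient's exposure stops at the first AE. If that rate is shown for related AEs, each of the D patients adds one to the numerator and shortens the denominator, so the rate also moves upward.

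**Step 4. Size.** D depends on how often laboratory results are judged clinically significant, how many of those would otherwise be rated not related, and how many sites follow the sentence. None of the three is in the documents.

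**The case against.** The strongest reply is that this is a slip of the pen. The words introducing the second clause are conditional, which suggests that *whether* was dropped before *related*. The reference to previous use in Open-HART points to findings around the VTV, when patients already on drug sign a new consent and could be misclassified under the pre-treatment definition in Section 7.1.2. On that reading the sentence is a narrow safeguard. This is plausible and probably the intent. It does not rescue the text: the printed words say the opposite, nothing limits them to the VTV, and even with *whether* restored the clause would still hang treatment-emergence on relatedness.

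A reader might infer that on-drug abnormalities judged unrelated fall out of the treatment-emergent set. The documents do not support this. Section 6.3.2 never states the converse, Sections 7.1.3 and 8.9.2 do not use causality, SAP Section 7.3 selects by date whatever the relationship, and the SAP introduction says the SAP prevails where the two differ. That precedence settles which AEs are tabulated. It does not settle the causality conflict, because the SAP takes the investigator's rating as it finds it.

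A reader might also try to size the bias by counting out-of-range electrolyte values expected by chance. That counts values, whereas the related-AE table counts AEs that passed the clinical-significance judgement. It would also need an assumed abnormality rate and independence between serial results in one patient, which is doubtful, and it would use a visit schedule that was not put into effect. It does not estimate the inflation.

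Finally, SAP Section 2.1 says the SAP rests on Amendment 04 and that Amendment 05 was not implemented. This objection stands: the current text does not show whether the sentence was in force when ratings were made. The expedited-reporting consequence is also narrow, since an event must still be serious and unexpected, and the error would be over-reporting.

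**Conclusion.** The concern holds as an internal contradiction. Section 6.3.2 presets causality against Section 7.2.2.3 and makes treatment-emergence sound like a result of relatedness, against Sections 7.1.3 and 8.9.2. The consequence is conditional: if sites follow the printed words, laboratory AEs are rated related by default, the related-AE summaries in protocol Section 8.9.2 and SAP Section 7.3 are biased upward, and the rules that turn on relatedness may be triggered.

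The direction is known and the size is not. The all-AE tables are unaffected provided the same events are recorded as AEs, that is, provided sites keep the clinical-significance filter. It would go too far to say that the collected ratings are biased, because that needs the sentence to have stood in Amendment 04 and to have been followed, and the documents show neither.

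**What to change.** Replace the sentence in Section 6.3.2 with:

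> Clinically significant abnormal laboratory results are recorded as AEs; their relationship to IMP, including prior pridopidine use in Open-HART, is rated case by case under Section 7.2.2.3; and they are treatment-emergent by timing or worsening under Section 7.1.3, regardless of relationship.

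This keeps the probable purpose, which is that earlier exposure counts when causality is judged, and removes both contradictions.

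The sponsor should also check whether Amendment 04 contained the same sentence. If it did, the ratings of laboratory AEs should be reviewed before the related-AE summary is relied on, and the clinical study report should say how they were made. If it did not, only the wording needs correcting.

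The cost is one sentence of protocol or site guidance and one document check, with no new data and no change to dosing or clinical management. Where sites would have followed the printed wording, fewer laboratory AEs will be labelled related.

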#### **6.3.3 Pregnancy Test**

Women of childbearing potential should have a pregnancy test performed and results confirmed before study drug administration at the VTV, RV1, and annually thereafter as well as at EOT, EOS/ET, and USVs, as needed.

#### **6.4 Vital Signs and Physical Examination**

Systolic and diastolic blood pressure and heart rate must be measured by mobile nurses at VTV and all remote visits as well as at EOT, EOS/ET, and USVs, as needed. Physical examination will be performed at the VTV only.

#### **6.5 Body Weight**

Patients must be weighed lightly clothed by mobile nurses at the VTV and all remote visits as well as at EOT, EOS/ET, and USVs, as needed.

### **7 SAFETY PARAMETERS AND ADVERSE EVENTS**

#### **7.1 Definitions**

##### **7.1.1 Adverse Event (AE)**

An AE is defined as any untoward medical occurrence in a patient or clinical study subject administered a medicinal product and which does not necessarily have a causal relationship with this treatment. An AE can therefore be any unfavorable and unintended sign (including an abnormal laboratory finding), symptom, or disease temporally associated with the use of a medicinal (investigational) product, whether or not related to the medicinal (investigational) product.

This definition includes accidental injuries, study drug intolerance, overdosing, reasons for any unplanned change in medication (drug and/or dose), reasons for any medical, nursing or pharmacy consultation, or reasons for admission to hospital or surgical procedures. It also includes AEs commonly observed and AEs anticipated based on the pharmacological effect of the IMP. In addition, any laboratory abnormality assessed as clinically significant by the investigator (or qualified designee) must be recorded as an AE.

##### **7.1.2 Pre-Treatment Adverse Event**

A pre-treatment AE is any untoward medical occurrence arising or observed between informed consent and start of IMP.

##### **7.1.3 Treatment-Emergent Adverse Event**

A treatment-emergent AE is any AE occurring after start of IMP and within the time of residual drug effect, or a pre-treatment AE or pre-existing medical condition that worsens in intensity after start of IMP and within the time of residual drug effect.

The time of residual drug effect is the estimated period of time after the last dose of the IMP, where the effect of the product is still considered to be present based on PK, pharmacodynamics, or other IMP characteristics. The time of residual drug effect is for most drugs 5 half-lives of the IMP.

##### **7.1.4 Overdose**

A drug overdose is the accidental or intentional use of a drug or medicine in an amount that is higher than the recommended daily dose. In the context of this study, this is defined as any dose above 90 mg pridopidine (TV-7820) daily.

---

## **7.2 Collection and Recording of Adverse Events**

### **7.2.1 Collection of Adverse Events**

The investigator (or qualified designee) must monitor the condition of the patient throughout the study from the time of obtaining informed consent until the EOS visit or end of follow-up period, as applicable.

AEs include:

- Patients positive response to questions about their health (at each visit, AEs will be elicited using a standard non-leading question such as "How have you been feeling since your last visit?")
- Symptoms spontaneously reported by the patient.
- Clinically relevant changes and abnormalities observed by the investigator (or qualified designee) (e.g. local and systemic tolerability, laboratory measurements, results of physical examinations, etc.).

If a patient suffers from the same AE more than once and the patient recovers in between the events, the AEs should be reported separately.

The investigator (or qualified designee) must record all AEs on the AE Log provided in each patient's eCRF with information about:

- AE
- Date of onset and time of onset
- Intensity
- Causal relationship to IMP
- Action taken to IMP
- Other action taken
- Date of outcome and time of outcome
- Outcome

Each of the items on the AE Log is described in detail in the following sections.

### **7.2.2 Adverse Event**

AEs should be recorded as diagnoses, if available. If not, separate sign(s) and symptom(s) are recorded. Only one diagnosis/symptom should be entered per record.

Pre-existing clinically significant conditions diagnosed or observed as a result of the screening procedures must be recorded as AEs. However, pre-existing, known clinically significant conditions observed at screening should be recorded as medical history.

The following exceptions should be noted when recording AEs:

- Death is not an event but the cause of death is. An exception is the event of sudden death of unknown cause.
- Hospitalization is not an event but the reason for hospitalization is.
- Procedures are not events, the reasons for conducting the procedures are. In general, only the reason for conducting the procedure will be captured as an AE. However, if deemed necessary by the investigator (or qualified designee), a procedure can be captured along with the reason for conducting the procedure. E.g. if the procedure "eye surgery" was performed due to "diabetic retinopathy", "diabetic retinopathy" (the reason) must be recorded as an AE, and if the investigator (or qualified designee) assess it is of importance, "eye surgery" can be entered as an additional AE.

- Overdoses and medication errors with or without clinical consequences should be recorded as AEs. In the presence of clinical consequences these should be reported as "XXXX due to overdose". In the absence of clinical consequences this should be specified (e.g. overdose, no AE observed)
- Pre-planned hospitalization for a pre-existing condition that has been planned prior to the start of the study should not be recorded as an AE.
- Pregnancy

### 7.2.2.1 Date of Onset/Time of Onset

The date/time of onset of the AE is the day the first signs or symptoms of the event appeared (regardless of seriousness). For abnormal clinically significant laboratory values or an outcome of an examination, the date of onset is the day when the sample was taken or the examination performed. For pre-existing clinically significant conditions diagnosed or observed as a result of the screening procedures, the date of onset is the date of the procedure/observation. If an exact date is not available, the best possible estimate should be reported (e.g. in mid-January, 3 weeks ago, etc.).

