### **5.3 Dosage and Administration**

The dose in this study is 45 mg bid. The IMP should be swallowed whole with water. Sufficient IMP will be provided to allow 100% compliance between visits.

The IMP will be dispensed in-person at the VTV and in DTP shipments at 3-month intervals thereafter. Patients may be offered to take the first dose at the investigational center.

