## **8.4 Sample Size and Power Considerations**

As this is an open-label extension study, no sample size calculations have been performed.

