## 2. STUDY DESIGN

### 2.1. General Design

Note: the SAP is based on Protocol Am 04 (dated 25 August 2016), and that Protocol Am 05 was issued (on 29 June 2017) for study virtualization but was not implemented.

This is a multi-center open-label study of pridopidine 45mg bid for patients who completed the ACR16C009 (HART) or TV7820-CNS-20002 (PRIDE-HD) studies.

At the **Baseline Visit** the following tests will be performed and documented: review and completion of informed consent; review of inclusion and exclusion criteria; pregnancy test (for females of childbearing potential); review of (baseline) adverse events (AEs), concomitant medication and medical history. All patients will be assessed for suicidality using the Columbia-Suicide Severity Rating Scale (C-SSRS). Evaluation for Research Study Consent and blood draw (calcium, magnesium, potassium, and creatinine for creatinine clearance calculation) will be performed for patients from the PRIDE-HD study.

The following assessments will be performed: physical examination including vital signs (heart rate and blood pressure) and weight; review of concomitant medication; (including inquiry about changes in use of benzodiazepines and antidepressants); inquiry about changes in use of alcohol and illicit drugs; UHDRS (including motor assessment, cognitive assessment, behavioral assessment, functional capacity, independence scale, functional assessment); 12-lead electrocardiogram (ECG) (single).

Trial medication will be dispensed and an appointment made for the next visit.

At **Telephone Visit 1 (T1, Week 1)** an evaluation for research study consent will be conducted, any AEs will be collected and reported, compliance will be confirmed, concomitant medication reviewed (including inquiry about changes in use of benzodiazepines and antidepressants); inquiry about changes in use of alcohol and illicit drugs, C-SSRS, abbreviated Problem-Behaviors Assessment-Short Form (PBA-s), and an appointment for next contact will be made. Evaluation for Research Study Consent will be performed for patients from the PRIDE-HD study.

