#### **4.5. Study Days and Visits**

Study days are numbered relative to the first day of study drug administration. The start of treatment (Day 1) is defined as the date on which a patient takes the first dose of study drug, as recorded on the study drug diary. Days will be numbered relative to treatment start (ie, ..., -2, -1, 1, 2, ...; with day 1 being the first day of study drug administration and day -1 being the day before the first day of study drug administration).

For efficacy and safety by-visit analyses, data collected at postbaseline scheduled visits will be included using their scheduled visit, data collected at postbaseline unscheduled visits will be included and assigned to their corresponding scheduled visit, and data collected at early termination visits will be included and assigned to the next scheduled visit. After the assignments are made, if there is a scheduled and unscheduled visit at the same visit, the scheduled visit will be used in the analysis.

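### SAP 7.3 counts AEs by calendar day, so a pre-existing condition found before the first dose on the same day enters the on-treatment tables

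*Protocol*

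**What the plan says.** **Recording.** Protocol 7.2.2: "Pre-existing clinically significant conditions diagnosed or observed as a result of the screening procedures must be recorded as AEs". Conditions that were already known go to medical history instead.

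**Dating.** Protocol 7.2.2.1 sets the onset of these AEs by rule: if "diagnosed or observed as a result of the screening procedures, the date of onset is the date of the procedure/observation". Clinically significant laboratory or examination results likewise take the date of the sample or examination.

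**Protocol classification.** Section 7.1.2 treats anything that arises or is observed between consent and the start of study drug as a pre-treatment AE. Section 7.1.3: "A treatment-emergent AE is any AE occurring after start of IMP and within the time of residual drug effect"; it adds earlier conditions that worsen after the start. Section 8.9.2 also works from events that start after the first dose.

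**SAP counting.** SAP 7.3: "AEs occurring on or after the first day of study drug administration will be included in the summaries". SAP 4.5: "The start of treatment (Day 1) is defined as the date on which a patient takes the first dose of study drug". In the exposure-adjusted rate of SAP 7.3, a patient with an AE contributes exposure only up to the day of the first one.

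**Timing.** At the Baseline Visit in SAP 2.1, eligibility, baseline AEs, physical examination and ECG are covered, and blood is drawn for patients from PRIDE-HD. At the same visit, "Trial medication will be dispensed and an appointment made for the next visit". Protocol 5.3 adds: "Patients may be offered to take the first dose at the investigational center".

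**Precedence.** The SAP introduction gives the SAP priority where the two documents differ. SAP Section 9 declares no changes from the protocol's analyses.

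**The concern.** An AE whose onset date is the date of a baseline procedure describes the patient before the first dose in this study. If that date is also Day 1, a rule based on the day alone cannot separate it from an event that began after dosing. Four outputs are affected:

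- Crude incidence of the preferred term and its system organ class gains a patient.
- The exposure-adjusted rate gains a full event and at most one day of exposure. The patient's later time at risk for that term is lost.
- Patients count once per preferred term, so a later true worsening under the same term adds nothing to incidence or rate. It would show only in the severity table, and only if it was more severe.
- The first period of the summary of AEs by time on treatment is loaded with findings that were already there.

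The SAP is also at odds with itself. SAP 4.2 takes as baseline the last value before the first dose. An ECG recorded on Day 1 before dosing is therefore the baseline for the shift table in SAP 7.5, while an AE raised from that same ECG is on-treatment under SAP 7.3. Long-term safety is a primary objective, and with no control arm nothing in the tables would reveal the misclassification.

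**Working it through.** The documents give no figure on this point (Protocol 8.4: "As this is an open-label extension study, no sample size calculations have been performed"), so there is nothing to reproduce. The check is a date trace and then an illustration.

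**Date trace**

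1. A baseline procedure on date P finds a previously unknown, clinically significant condition. It is recorded as an AE (Protocol 7.2.2) with onset P (7.2.2.1).
2. The first dose is taken on date D, so Day 1 = D (SAP 4.5).
3. SAP 7.3 includes the AE if P ≥ D.
4. If D is later than P, the AE falls before Day 1 and is left out, as it should be.
5. If D = P, the AE is included although it was observed before dosing. Under Protocol 7.1.2 it is pre-treatment.

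The error arises only in step 5.

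**Illustration.** The inputs are assumptions, except N and the rate formula:

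- N = 47 is the patient number in the Protocol 1.1 synopsis. The size of the SAP's safety analysis set is not given.
- F is the follow-up per patient: 1, 3 or 5 years.
- t is the number of patients with a true on-treatment event in one preferred term, placed at F/2: 1, 2 or 5.
- k is the number of patients with a misdated Day 1 finding in that term, each with one day of exposure: 1 or 3.

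Crude incidence = (t + k)/N. Each misdated patient adds 1/47 = 2.1 percentage points.

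Rate (SAP 7.3) = (t + k) / [(N − t − k)F + tF/2 + k/365.25]

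With F = 3 and t = 2:

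- k = 0: 2/(45×3 + 2×1.5) = 2/138.0 = 1.45 per 100 patient-years
- k = 1: 3/(44×3 + 3 + 0.003) = 3/135.0 = 2.22 per 100 patient-years
- k = 3: 5/(42×3 + 3 + 0.008) = 5/129.0 = 3.88 per 100 patient-years

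For F = 3 years (rates per 100 patient-years):

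| True cases | Misdated | Incidence without / with | Rate without / with | Ratio of rates |
|---|---|---|---|---|
| 1 | 1 | 2.1% / 4.3% | 0.72 / 1.47 | 2.04 |
| 2 | 1 | 4.3% / 6.4% | 1.45 / 2.22 | 1.53 |
| 5 | 1 | 10.6% / 12.8% | 3.75 / 4.60 | 1.23 |
| 1 | 3 | 2.1% / 8.5% | 0.72 / 3.06 | 4.28 |
| 2 | 3 | 4.3% / 10.6% | 1.45 / 3.88 | 2.67 |
| 5 | 3 | 10.6% / 17.0% | 3.75 / 6.43 | 1.72 |

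To two decimals the ratios are the same at 1, 3 and 5 years. The distortion is largest for uncommon terms.

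**The case against.** Much of the case on the other side stands, and it sets the limits of the point.

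- **Protocol version.** SAP 2.1 says that the SAP rests on Amendment 04 and that Amendment 05 was not implemented. The supplied protocol is the Amendment 05 text. Its sentence on taking the first dose at the centre follows one about the Virtual Transition Visit, when patients are already in Open-HART. That Sections 5.3, 7.2.2 and 7.2.2.1 read the same in Amendment 04 is an assumption, though talk of screening and a first dose fits the entry visit better.
- **Screening visit.** SAP 2.1 describes none, but SAP 5.2, 5.5 and 7.8 mention screening, and the supplied text does not show the schedule in Protocol 1.2. If screening came on an earlier day, its findings fall before Day 1 and are not counted.
- **Few eligible findings.** Protocol 4.5 excludes patients with QTcF above 450 ms, creatinine clearance below 60 mL/min, or significant laboratory results that affect suitability. Known conditions are medical history. SAP 2.1 describes baseline bloods only for patients from PRIDE-HD.
- **Earlier exposure.** A reader might infer that these records describe patients who had never had the drug. They do not: many took pridopidine in HART or PRIDE-HD. Protocol 6.3.2 treats as treatment-emergent those abnormal laboratory results that the investigator relates to earlier use in Open-HART. Deleting every pre-dose finding could hide a carry-over effect.
- **Data.** A reader might infer that the correction needs nothing beyond what is collected. The AE log in Protocol 7.2.1 has a time of onset but no visit field, and SAP 4.5 mentions the date of first dose but not its time.
- **Direction.** The rule errs towards over-counting in a descriptive, single-arm study. That is cautious for crude counts. It does not excuse a shortened exposure, a masked later worsening, or an undeclared departure from the protocol.

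**Conclusion.** The point holds in a narrow form. SAP 7.3 has no means of keeping out an AE that was observed before the first dose but dated to the same day. That conflicts with Protocol 7.1.2, 7.1.3 and 8.9.2, and SAP Section 9 does not declare the difference. Because the SAP prevails, the calendar-day rule would govern the safety tables.

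The conclusion rests on two conditions: that the Amendment 05 wording also applied under Amendment 04, and that some patients had their screening procedures and first dose on one day. It covers only clinically significant, non-excluding, previously unknown findings.

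The size is unknown. A reader might infer from the illustration that the AE tables are materially inflated. The documents do not support that, because they give neither the share of same-day starts nor the number of such findings. What can be said is that, at an assumed 47 patients, each affected patient adds 2.1 percentage points to a term's incidence. With 1 to 5 true cases, one such patient multiplies the term's exposure-adjusted rate by 2.04 to 1.23. The change should be made: the rule conflict is real, it touches a primary objective, and it is cheap to remove.

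**What to change.** In SAP 7.3:

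1. Define AEs for the on-treatment tables as the protocol does: onset, or worsening of an earlier condition, after the first dose.
2. Classify a Day 1 AE as pre-treatment where the records show that it was observed before the first dose. The evidence is the baseline AE review, or onset time against first-dose time where both exist.
3. List these AEs separately and leave them out of the on-treatment tables and rates unless they worsen after the first dose.
4. Keep Day 1 AEs whose order relative to the first dose is unknown in the on-treatment set.
5. Keep abnormal laboratory results that the investigator relates to earlier pridopidine use visible in the separate listing.

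If the sponsor prefers to keep the calendar-day rule, SAP Section 9 should declare it as a change from Protocol 7.1.2, 7.1.3 and 8.9.2.

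The cost is a short SAP text change, one derivation flag and one listing. The downside is some reliance on incomplete time data. Item 4 limits this by leaving unresolved cases where the present rule puts them, and the listing keeps every removed record in view.
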